14.2.3. Analysis

Table 14.3.1.20: Non-drug related therapies

Number (percent) of subjects per treatment group classified per system organ class and preferred term.

Population: safety analysis set.

Listing 16.2.10.14: Non-drug related therapies

Listing per treatment group and per subject of all non-drug therapy records.

When these records are linked to medical history or adverse events, these additional details (reported term of the medical history condition(s) or reported term of the adverse event(s), including their record ID numbers) will be printed as well.

Population: safety analysis set.

14.3. LABORATORY SAFETY

14.3.1. Available Data

Laboratory parameters expected are described in the protocol (section 6.5.2 of the protocol). Only central laboratory data will be included.

14.3.2. Number of Significant Digits

The standardized results of continuous laboratory parameters, as well as their standardized normal limits, will be mapped to analysis values and analysis normal limits without rounding.

Only for printing in the analysis TLFs, a maximum of 3 decimal positions will be shown.

14.3.3. Categorization of Laboratory Parameters

Laboratory parameters will be presented grouped into three main categories: biochemistry, hematology and coagulation. Urinalysis, serology, cytokines and pregnancy test will be only listed. All central lab data will be listed even unscheduled lab category/parameter.

14.3.4. Derivation of Laboratory Parameters

NAP.

14.3.5. Baseline and Change from Baseline

The baseline is defined as the last sample prior to the first dose of study medication. Baseline will be determined per lab test individually. It is recognized that baseline tests may thus come from more than one lab sample and not just from the “baseline visit” sample.

The change from baseline will be calculated for all post-baseline time points as:

Change from baseline at time point t = value at time point t – baseline value.

14.3.6. Scoring of Laboratory Values

14.3.6.1. Scoring According to Normal Ranges

The position of the actual analysis values versus their normal ranges will be determined directly using the position indicator provided in the database as reported by the laboratory (lbrind), expressing the classes for these analysis values as low (L), normal (N) or high (H).

14.3.6.2. According to CTCAE Grades

CTCAE version 4.03 classification is only for the below tests. For other tests, only the classification according to normal ranges will be done.

Chemistry:

| Laboratory test | Grade 0 | Grade 1 | Grade 2 | Grade 3 | Grade 4 |
|---------------------------------|---------|-----------------|-----------------|------------------|--------------|
| Albumin (g/L) | ≥ LLN | [30,LLN[| [20,30[| <20 | (NAP) |
| ALT (U/L) | ≤ ULN |]1.0,3.0] x ULN |]3.0,5.0] x ULN |]5.0,20.0] x ULN | > 20.0 x ULN |
| AST (U/L) | ≤ ULN |]1.0,3.0] x ULN |]3.0,5.0] x ULN |]5.0,20.0] x ULN | > 20.0 x ULN |
| Alkaline phosphatase (U/L) | ≤ ULN |]1.0,2.5] x ULN |]2.5,5.0] x ULN |]5.0,20.0] x ULN | > 20.0 x ULN |
| GGT (U/L) | ≤ ULN |]1.0,2.5] x ULN |]2.5,5.0] x ULN |]5.0,20.0] x ULN | > 20.0 x ULN |
| Total bilirubin (μmol/L) | ≤ ULN |]1.0,1.5] x ULN |]1.5,3.0] x ULN |]3.0,10.0] x ULN | > 10.0 x ULN |
| Calcium low (mmol/L) | ≥ LLN | [2.00,LLN[| [1.75,2.00[| [1.50,1.75[| <1.50 |
| Calcium high (mmol/L) | ≤ ULN |]ULN,2.9] |]2.9,3.1] |]3.1,3.4] | >3.4 |
| Total cholesterol (mmol/L) | ≤ ULN |]ULN,7.75] |]7.75,10.34] |]10.34,12.92] | >12.92 |
| Creatinine (μmol/L) | ≤ ULN |]1.0,1.5] x ULN |]1.5,3.0] x ULN |]3.0,6.0] x ULN | > 6.0 x ULN |
| Creatinine kinase | ≤ ULN |]1.0,2.5] x ULN |]2.5,5.0] x ULN |]5.0,10.0] x ULN | > 10.0 x ULN |
| Glucose low (mmol/L) | ≥ LLN | [3.0,LLN[| [2.2,3.0[| [1.7,2.2[| <1.7 |
| Glucose high (mmol/L) [fasting] | ≤ ULN |]ULN,8.9] |]8.9,13.9] |]13.9,27.8] | >27.8 |
| Phosphate (mmol/L) | ≥ LLN | [0.8,LLN[| [0.6,0.8[| [0.3,0.6[| <0.3 |
| Potassium low (mmol/L) | ≥ LLN | [3.0,LLN[| (NAP) | [2.5,3.0[| <2.5 |
| Potassium high (mmol/L) | ≤ ULN |]ULN,5.5] |]5.5,6.0] |]6.0,7.0] | >7.0 |
| Sodium low (mmol/L) | ≥ LLN | [130,LLN[| (NAP) | [120,130[| <120 |
| Sodium high (mmol/L) | ≤ ULN |]ULN,150] |]150,155] |]155,160] | >160 |
| Triglycerides (mmol/L) | < 1.71 | [1.71,3.42] |]3.42,5.7] |]5.7,11.4] | > 11.4 |

Hematology:

| Laboratory test | Grade 0 | Grade 1 | Grade 2 | Grade 3 | Grade 4 |
|-------------------------------------|---------|-----------|-----------|-----------|---------|
| Hemoglobin (g/L) | ≥ LLN | [100,LLN[| [80,100[| < 80 | (NAP) |
| WBC (giga/L) | ≥ LLN | [3.0,LLN[| [2.0,3.0[| [1.0,2.0[| <1.0 |
| Lymphocyte count decreased (giga/L) | ≥ LLN | [0.8,LLN[| [0.5,0.8[| [0.2,0.5[| < 0.2 |
| Lymphocyte count increased (giga/L) | (NAP) | (NAP) |]4,20] | >20 | (NAP) |
| Neutrophils (giga/L) | ≥ LLN | [1.5,LLN[| [1.0,1.5[| [0.5,1.0[| < 0.5 |
| Platelet count (giga/L) | ≥ LLN | [75,LLN[| [50,75[| [25,50[| < 25 |

Coagulation:

| Laboratory test | Grade 0 | Grade 1 | Grade 2 | Grade 3 | Grade 4 |
|---|---------|-----------------|-----------------|-------------|---------|
| Activated Partial thromboplastin time (s) | ≤ ULN |]1.0,1.5] x ULN |]1.5,2.5] x ULN | > 2.5 x ULN | (NAP) |
| INR | ≤ ULN |]1.0,1.5] x ULN |]1.5,2.5] x ULN | > 2.5 x ULN | (NAP) |
| Laboratory test | Grade 0 | Grade 1 | Grade 2 | Grade 3 | Grade 4 |
| Activated Partial thromboplastin time (s) | ≤ ULN |]1.0,1.5] x ULN |]1.5,2.5] x ULN | > 2.5 x ULN | (NAP) |

Note:

- LLN = lower normal limit,
- ULN = upper normal limit,
- (NAP) = grade does not exist.

14.3.7. Treatment-emergent Principle

14.3.7.1. Toxicity Grades

A post-baseline toxicity grade 1, 2, 3 or 4 is defined as treatment-emergent when higher than the toxicity grade of the baseline result. If the baseline result is missing, a post-baseline toxicity grade 1, 2, 3 or 4 will always be considered as treatment-emergent.

14.3.7.2. Non-graded Abnormalities

A post-baseline non-graded abnormality class L or H is defined as treatment-emergent when it differs from the abnormality class of the baseline result. If the baseline result is missing, a post-baseline abnormality L or H will always be considered as treatment-emergent.

14.3.8. Determination of Worst-case Abnormality

14.3.8.1. According to Normal Range

The worst-case post-baseline result position versus normal range (L/N/H) will be determined per subject and per parameter.

The following worst-cases will be determined, using all non-missing post-baseline records (including unscheduled and follow-up visits):

- H = high:
At least one post-baseline result is classified as H, and there are no results classified as L.
- L = low:
At least one post-baseline result is classified as L, and there are no results classified as H.
- H+L = high and low:
At least one post-baseline result is classified as H, and at least another post-baseline result is classified as L.
- N = normal: All post-baseline results are classified as N.

14.3.8.2. According to CTCAE Grades

The worst-case post-baseline toxicity grade 0, 1, 2, 3 or 4 will be determined per subject and per parameter (and direction, if below and above), using all non-missing post-baseline records (including unscheduled and follow-up visits).

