6.5. Safety Assessments

This section describes methods and timing for all safety assessments and recording. Additional assessments (e.g. unscheduled clinical laboratory tests or extra vital signs recordings) are allowed to ensure appropriate collection of safety data and to assess any perceived safety concerns.

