6.5.2. Clinical Laboratory Evaluations

The following clinical laboratory safety tests will be performed:

- Hematology: hematocrit, hemoglobin, red blood cell count, white blood cell count, white blood cell differential count (absolute and relative), and platelets.

- Clinical chemistry: glucose, urea, creatinine, uric acid, sodium, potassium, calcium, chloride, phosphorus, AST, ALT, GGT, total bilirubin, alkaline phosphatase, albumin, total proteins, triglycerides, cholesterol, high density lipoprotein, low density lipoprotein, C-reactive protein, and total IgE.
- Urinalysis: proteins (semi-quantitative) and ketones can be tested via standard test strip; microscopic examination of the sediment (cylinders, erythrocytes, leukocytes) if indicated (when the test strip was positive for blood and/or proteins).
- Serology (only at screening): HBs antigen, HBc antibody, and hepatitis C antibody, and HIV 1 and 2. Positive hepatitis, and HIV results should be reported by the investigator as required by local law.
- Pregnancy test for females of childbearing potential: serum beta human chorionic gonadotropin at screening, urine dipstick before dosing on Day 1 and at all time points thereafter. In case of doubt, determination of FSH can be done at the central laboratory to confirm menopause.

The clinical laboratory evaluations will be performed at visits specified in the Schedule of Activities in Section 6.10 (see also Section 6.1, "Timing of Assessments"). On dosing days, blood and urine samples will be collected prior to dosing. Blood sampling for clinical lab should be done in fasting conditions (for at least 8 hours). Results from the screening visit will be used for the inclusion/exclusion criteria on the baseline visit (Day 1).

Reference ranges will be supplied by the central laboratory. Clinical laboratory values outside the normal range will be flagged and clinical relevance will be assessed by the investigator. Only laboratory test abnormalities judged as clinically significant by the principal investigator should be recorded as AEs.

Retesting of clinical laboratory screening tests is allowed once only for technical reasons (e.g. sample hemolyzed, out of stability or late arrival at central laboratory). Retesting of laboratory tests for safety or if medically indicated in the opinion of the investigator is always allowed.

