6. SELECTION OF DATA RECORDS FOR ANALYSIS

All reported events, and all assessments without missing results will be used in the statistical analysis. However, the next specific exclusions will be done in some specific applications.

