14.3.12. Listings

Next to the actual values and the changes from baseline, all listings will present the following parameters:

- The sample date and time;
- The subject's fasting status for the laboratory sample (Y or N);
- The value abnormality (result position versus normal range, L or H);
- The CTCAE toxicity grade (where applicable)
- The normal range associated to the parameter value;
- Any related comments.

Listing 16.2.11.1: Laboratory data: Full listing

Listing per treatment group, per subject, parameter and analysis visit/time point of all data.

Population: safety analysis set.

Listing 16.2.11.2: Laboratory data: Listing of treatment-emergent abnormalities

Listing per treatment group, per subject and per time point of all post-baseline time points scored as treatment-emergent (normal ranges and toxicity grades), plus also the baseline reference time point.

Population: safety analysis set.

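### High glucose is graded on a scale labelled fasting, but no rule keeps non-fasting samples out of the baseline, treatment-emergent or worst-case grade, although fasting status is recorded

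*SAP*

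**What the plan says.** **Grading scale.** SAP 14.3.6.2 restricts CTCAE grading to the tests it tabulates. One row is "Glucose high (mmol/L) [fasting", with a closing bracket after the last word: Grade 1 runs from above the ULN to 8.9 mmol/L, Grade 2 to 13.9, Grade 3 to 27.8, and Grade 4 lies above that. The low-glucose row has no such label, nor does the triglyceride row ("Triglycerides (mmol/L) | < 1.71 | [1.71,3.42" for Grades 0 and 1).

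**Which records count.** SAP 14.3.8.2 takes the worst grade per subject and parameter "using all non-missing post-baseline records (including unscheduled and follow-up visits". SAP section 6 sets the general default: "All reported events, and all assessments without missing results will be used in the statistical analysis". It then allows specific exclusions, and none of those in 6.1 to 6.4 concerns fasting.

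**Baseline and emergence.** SAP 14.3.5 takes the most recent pre-dose sample for each test, fasting or not. SAP 14.3.7.1 states: "A post-baseline toxicity grade 1, 2, 3 or 4 is defined as treatment-emergent when higher than the toxicity grade of the baseline result". With no baseline result, every post-baseline Grade 1 to 4 counts as treatment-emergent.

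**Fasting.** Protocol 6.5.2 says "Blood sampling for clinical lab should be done in fasting conditions (for at least 8 hours". SAP 14.3.12 prints "The subject's fasting status for the laboratory sample (Y or N" in the laboratory listings. The SAP makes no other use of that variable. Protocol 6.5 adds: "Additional assessments (e.g. unscheduled clinical laboratory tests or extra vital signs recordings) are allowed".

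**The concern.** The scale and the selection rule do not match. The label says that the graded quantity is fasting glucose, but the rule admits any glucose. Because fasting status is printed as Y or N, the plan itself allows for some samples being non-fasting. These could be scheduled draws where the subject had eaten, or unscheduled draws that happen to include glucose.

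A worst-case rule needs only one record, so a single post-meal value can put a subject in Grade 1 or 2 of a fasting scale. The affected outputs are the worst-case grades (Table 14.3.2.4), the shifts from baseline grade (14.3.2.5) and the treatment-emergent grades (14.3.2.6). With 40 and 20 subjects planned, one altered subject moves an arm's percentage by 1/40 = 2.5 points or 1/20 = 5 points.

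**Working it through.** The plan states no figure on this point, so there is none to reproduce. The check has three parts: is there a fasting filter anywhere, what do the printed limits do to a non-fasting value, and how many subjects could be exposed.

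**1. Search for a filter.** The visit windows and selection rules (SAP 5.2, 5.3), record exclusions (6.1 to 6.4), missing-data rules (7.1) and the laboratory section (14.3) contain none. Fasting appears in the SAP only as the row label in 14.3.6.2 and the listing item in 14.3.12.

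**2. Effect of the printed limits.** The values below are illustrative. The ULN for glucose is not given; I assume 5.6 to 6.1 mmol/L, and the results are the same across that range.

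| Case | Records | Result as written | Fasting samples only |
|---|---|---|---|
| Glucose, grade set | Eight fasting values of 5.2, plus one non-fasting 7.5 | Worst grade 1 | Grade 0 |
| Glucose, grade set | Eight fasting values of 5.2, plus one non-fasting 9.2 | Worst grade 2 | Grade 0 |
| Glucose, grade masked | Fasting screening 5.2; non-fasting Day 1 baseline 7.5; fasting post-baseline 7.0 | Baseline grade 1, post-baseline grade 1: not treatment-emergent | Baseline grade 0, post-baseline grade 1: treatment-emergent |
| Triglycerides | Eight fasting values of 1.4, plus one non-fasting 3.6 | Worst grade 2 | Grade 0 |

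The first two glucose cases and the triglyceride case are treatment-emergent if the baseline grade is 0. The masking case shows that the error can run in either direction in the shift and treatment-emergent tables. Only for the worst-case grade in Table 14.3.2.4 is it upward alone.

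**3. Possible exposure.** SAP 5.2 gives eight scheduled post-baseline laboratory time points: Days 15, 29, 43, 57, 85, 127, 155 and 169. Let p be the chance that one draw is non-fasting, independent across draws. The documents do not give p. The chance that a subject has at least one non-fasting scheduled sample is 1 − (1 − p)^8.

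| Assumed p | 1 − (1 − p)^8 | Expected number of 60 subjects |
|---|---|---|
| 1% | 1 − 0.99^8 = 7.7% | 4.6 |
| 2% | 1 − 0.98^8 = 14.9% | 9.0 |
| 5% | 1 − 0.95^8 = 33.7% | 20.2 |
| 10% | 1 − 0.90^8 = 57.0% | 34.2 |

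These are chances of having such a sample, not of a changed grade. A changed worst grade also needs the non-fasting value to cross a grade limit that none of that subject's fasting values crosses, and the documents give nothing from which to estimate that.

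**The case against.** **The label may already be the filter.** If the listed test is fasting glucose, a non-fasting result is not a listed test and gets no CTCAE grade, and 14.3.8.2 only picks among grades already assigned. This is a fair reading. But the SAP does not say so or say what becomes of a non-fasting result, and 14.3.8.2 asks for all records. Two programmers could build different tables, so a clarifying sentence is needed on either reading.

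**Fasting is already required.** The protocol instruction is not limited to scheduled visits, so what remains is non-compliance at an unknown rate. That stands, and it limits the size of the problem.

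**Liver-test retests as the source.** A reader might infer that confirmation draws or post-rechallenge monitoring supply the non-fasting values. The documents do not support this. The confirmation panel in Protocol 4.5.4 names neither glucose nor triglycerides, the repeat testing there concerns liver tests, Protocol 6.2 ties unscheduled assessments to the reason for the visit, and SAP 14.3.1 admits only central laboratory data. An unscheduled draw matters only if it includes glucose.

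**Triglycerides.** Treating those limits as fasting limits would be an inference from a sampling instruction that covers every blood test; the row carries no label. This objection stands, and the remedy for triglycerides is weaker for that reason.

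**A filter can do harm.** Dropping non-fasting values could remove very high results from view. An ungraded baseline treated as missing would turn every later graded result into a treatment-emergent one under 14.3.7.1. Both risks are real for a bare filter. They are met by keeping the values in the normal-range tables and listings, and by a fallback baseline: Protocol 6.3 calls for fasting samples at screening.

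**Low stakes.** Safety analysis is descriptive (SAP 14), the primary endpoint is TEAEs, SAEs and AESIs, and a reader of the listings can trace an affected grade. This stands.

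**Conclusion.** The mismatch is real for high glucose: the scale is labelled fasting, and the baseline, treatment-emergent and worst-case rules do not use the fasting status that is available. A non-fasting sample can therefore set or mask a grade in Tables 14.3.2.4 to 14.3.2.6. How often is unknown; the percentages above rest on assumed, independent non-fasting rates and measure exposure only. The effect on these supportive tables is probably small.

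Two stronger readings are tempting. One is that the tables will contain false grades, always in the upward direction. The documents show only that they can, and an unfiltered baseline can also hide a grade. The other is that the arm with more unscheduled visits will look worse. Nothing in the documents gives a reason to expect different non-fasting rates by arm, so no between-arm bias is shown.

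**What to change.** Add to SAP 14.3.6.2, and apply in 14.3.5, 14.3.7.1 and 14.3.8.2:

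- Assign the glucose-high CTCAE grade only to samples with fasting status Y.
- Take the baseline grade for this parameter from the last fasting pre-dose sample, which may be the screening sample.
- State how a missing fasting status is treated, and what happens when no fasting pre-dose sample exists, so that the missing-baseline rule in 14.3.7.1 does not apply by default.
- Keep non-fasting glucose values in the normal-range tables (14.3.2.2, 14.3.2.3) and, flagged, in the listings, so that no high value is lost.
- For triglycerides, keep the planned grading and add a fasting-only sensitivity version of Tables 14.3.2.4 to 14.3.2.6.

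Glucose-low and all other tests stay as planned. The cost is a few SAP sentences, one filter on a variable already in the data, and a sensitivity output for one parameter. The downside is that a few glucose records lose a CTCAE grade; a very high non-fasting glucose would appear in the tables only as above normal range, with its value in the listings.

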14.3.9. Handling of Categorical Laboratory Parameters

Categorical laboratory parameters (usually urinalysis) will only be listed. No determination of toxicity grades nor determination of worst-cases apply to these parameters.

14.3.10. Tables

Laboratory parameters with an overall low sample size (<2 observations looking at the whole study) will not be presented in tables, but only in listings.

All tables in this section will be presented per treatment group and analysis visit/time point.

Table 14.3.2.1: Laboratory data: Descriptive statistics of the actual values and change from baseline per time point

Descriptive statistics of the actual values and changes from baseline (including 95% CI of the mean for change from baseline values) per laboratory test category, parameter, treatment group and analysis visit/time point.

Population: safety analysis set.

Table 14.3.2.2: Laboratory data: Worst-case shift table according to the normal range

Shift table per laboratory test category, parameter and treatment group.

This table will present the shift in abnormality (L/N/H) for the worst-case versus the baseline abnormality (L/N/H).

Table for lab tests with normal ranges.

Population: safety analysis set.

Table 14.3.2.3: Laboratory data: Worst-case treatment-emergent laboratory abnormalities

Frequency table of the worst-case treatment-emergent abnormalities per laboratory test category, parameter and treatment group.

Table for lab tests with normal ranges.

Population: safety analysis set.

Table 14.3.2.4: Laboratory data: Worst-case CTCAE toxicity grades

Frequency table of the worst-case CTCAE toxicity grades (including cumulative percentages) per laboratory test category, laboratory test and treatment group.

Table for lab tests with CTCAE grading.

Population: safety analysis set.

Table 14.3.2.5: Laboratory data: Worst-case shift table of the CTCAE toxicity grades

This table will present the shift in CTCAE toxicity grade for the worst-case versus the CTCAE toxicity grade of the baseline result per laboratory test category, laboratory test and treatment group.

Table for lab tests with CTCAE grading.

Population: safety analysis set.

Table 14.3.2.6: Laboratory data: Worst-case treatment-emergent CTCAE toxicity grades

Frequency table of the worst-case treatment-emergent lab CTCAE toxicity grades per lab test category, lab test and treatment group.

Table for lab tests with CTCAE grading.

Population: safety analysis set.

14.3.11. Figures**Figure 14.3.2.1: Laboratory data: Mean (+/- SE) of the actual values over time**

Arithmetic mean with SE of the laboratory test results over time, with both treatment groups on the same plot (all study days/time points to be displayed on the same plot). Each laboratory parameter will be on a new plot.

Population: safety analysis set.

Figure 14.3.2.2: Laboratory data: Mean (+/- SE) of the changes from baseline over time

Arithmetic mean with SE of the laboratory test change from baseline results over time, with both treatment groups on the same plot (all study days/time points to be displayed on the same plot). Each laboratory parameter will be on a new plot.

Population: safety analysis set.

14.3.12. Listings

Next to the actual values and the changes from baseline, all listings will present the following parameters:

- The sample date and time;
- The subject's fasting status for the laboratory sample (Y or N);
- The value abnormality (result position versus normal range, L or H);
- The CTCAE toxicity grade (where applicable)
- The normal range associated to the parameter value;
- Any related comments.

Listing 16.2.11.1: Laboratory data: Full listing

Listing per treatment group, per subject, parameter and analysis visit/time point of all data.

Population: safety analysis set.

Listing 16.2.11.2: Laboratory data: Listing of treatment-emergent abnormalities

Listing per treatment group, per subject and per time point of all post-baseline time points scored as treatment-emergent (normal ranges and toxicity grades), plus also the baseline reference time point.

Population: safety analysis set.

